EQ-5D-3L	X		X	X	X	Patients should complete the assessment at the start of the clinic visit, prior to dosing and scheduled activities.
FKSI-19	X		X	X	X	
PRO-CTCAE	X		X	X	X	Completed on Days 1 and 22 of every cycle through Cycle 4, and then on Day 1 of the following cycles. See Section 7.6 for further details.

Abbreviations used in this table appear on the final page of [Table 4](#).

Table 3: On-Treatment Schedule of Events for Arm B (Contd)

Procedure ^a	Arm B Cabozantinib 60 mg PO once daily (continuously) OR Sunitinib 50 mg PO once daily (4 weeks on treatment, followed by 2 weeks off treatment) Cycle = 6 Weeks					Notes
	Cycle 1			Cycle 2 and subsequent on-treatment visits		
	Day 1	Day 8 (-1 day)	Day 22 (± 3 days)	Day 1 (± 3 days)	Day 22 (± 3 days)	
Health Care Resource Utilization	X		X	X	X	Site staff will collect the health care resource utilization data at each visit using the CRF.

a. Assessments and visits that occur outside of protocol-specified windows (e.g., for holidays, travel issues, insurance issues) may be acceptable on a case-by-case basis after review by the Medical Monitor.

Abbreviations used in this table appear on the final page of [Table 4](#).

Table 4: Long-Term Follow-Up Schedule of Events

Procedure ^a	Safety Follow-Up Visit 1 ^b	Safety Follow-Up Visit 2 ^b	Survival Follow-Up ^c Every 12 Weeks (± 14 days)	Notes ^d
Safety Assessments				
Vital Signs	X	X		Blood pressure, heart rate, temperature Weight
AE and SAE Assessments	X	X	X	All AEs will be documented until 100 days after the last dose of all study drug(s). SAEs to be collected after the 100-day safety visit if the SAE is deemed to be related or residual toxicities are persisting. Patients will be followed for drug-related toxicities until these toxicities resolve, return to baseline, or are deemed irreversible.
Karnofsky Performance Status	X	X		See Appendix 2 .
Review of Subsequent Medications and Anticancer Therapy	X	X	X	In Survival Follow-up, subsequent anticancer treatment only. Additional subsequent anticancer therapy details such as regimen, setting of the regimen, line of therapy, start date and end date of each regimen, best response to the regimen, and date of progression to subsequent anticancer therapies will be collected.
Laboratory Tests				
Pregnancy Test (WOCBP only)	X	X		Patients (WOCBP) will continue to follow instructions for methods of contraception through 5 months post treatment completion.
Clinical Lab Testing (central laboratory)	X	See Notes		During Safety Follow-up Visit 2 if toxicities are present. Refer to Section 8.15 for list of laboratory tests.
Pharmacokinetic and Biomarker Assessments				
Nivolumab PK Blood Samples (Arm A only)	X	X		See Section 5.9 for further details.

Abbreviations used in this table appear on the final page of the table.

Table 4: Long-Term Follow-Up Schedule of Events (Contd)

Procedure ^a	Safety Follow-Up Visit 1 ^b	Safety Follow-Up Visit 2 ^b	Survival Follow-Up ^c Every 12 Weeks (± 14 days)	Notes ^d
[REDACTED]	■	■		[REDACTED]
Tumor Tissue Sample	See Section 5.10			Optional upon disease progression
Efficacy Assessments				
Body Imaging	
 • Contrast-enhanced CT of the chest, contrast-enhanced CT or MRI of the abdomen, pelvis, and all known and suspected sites of disease. See Section 7.2 if patient has contraindications to contrast CT or MRI. • Imaging should continue every 9 weeks (± 7 days) from randomization through (and inclusive of) Week 54 and then every 12 weeks (± 7 days). • Tumor assessments will continue until both BICR and Investigator’s assessments of tumor images have determined progression. • Patients who are receiving study treatment beyond progression should continue scans until the criteria for treatment discontinuation are met and BICR-assessed progression has occurred. • Tumor assessments are no longer required if subsequent anticancer therapy is started, even if the patient has not yet progressed. • Use same imaging method as was used at screening. • Bone scans may be collected per local standards, if clinically indicated. Digital photography should be performed and submitted, if clinically indicated. 			
All study treatment decisions will be based on the Investigator’s assessment of tumor images. See Section 7.0 for further details.

Abbreviations used in this table appear on the final page of the table.

Table 4: Long-Term Follow-Up Schedule of Events (Contd)

Procedure ^a	Safety Follow-Up Visit 1 ^b	Safety Follow-Up Visit 2 ^b	Survival Follow-Up ^c Every 12 Weeks (± 14 Days)	Notes ^d
Brain Imaging	
 Patients with a history of brain metastasis or neurological symptoms should have MRI with and without contrast. See Section 7.2 if patient has contraindications to contrast MRI. Brain imaging assessments should be performed on same schedule as body tumor assessments, or as clinically indicated Tumor assessments will continue until both BICR and Investigator’s assessments of tumor images have determined progression. Patients who are receiving study treatment beyond progression should continue scans until the criteria for treatment discontinuation are met and BICR-assessed progression has occurred. Tumor assessments are no longer required if subsequent anticancer therapy is started, even if the patient has not yet progressed. Use same imaging method as was used at screening. 			All study treatment decisions will be based on the Investigator’s assessment of tumor images. See Section 7.0 for further details.
Survival Status			X	Survival Follow-up can be administered in person or by telephone, if needed.
Health Outcomes Assessments				
EQ-5D-3L	X			See Section 7.6 for further details.
FKSI-19	X			
PRO-CTCAE	X			
Health Care Resource Utilization	X			Study site staff should collect health care resource utilization data using the CRF.

AE = adverse event; BICR = blinded independent central review; CT = computed tomography; CRF = case report form; CVA = cerebrovascular accident; ECG = electrocardiogram; eCRF = electronic case report form; EQ-5D-3L = 3-level version of the EuroQol Group’s EQ-5D; FKSI-19 = Functional Assessment of Cancer Therapy (FACT) Symptom Index for Kidney Cancer; hCG = human chorionic gonadotropin; IMDC = International Metastatic RCC Database Consortium; IV = intravenous(ly); MRI = magnetic resonance imaging;

MUGA = multigated acquisition; PK = pharmacokinetic(s); PO = orally; PRO-CTCAE = Patient-Reported Outcomes version of the Common Terminology Criteria for Adverse Events; q3w = every 3 weeks; RCC = renal cell carcinoma; SAE = serious adverse event; TIA = transient ischemic attack; UPCR = urine protein creatinine ratio; VW = vital signs and weight only; WOCBP = women of childbearing potential

- a. Assessments and visits that occur outside of protocol-specified windows (e.g., for holidays, travel issues, insurance issues) may be acceptable on a case-by-case basis after review by the Medical Monitor.
- b. Patients must be followed for 100 days after the last dose of study treatment. Safety Follow-Up Visit 1 should occur 30 (\pm 7) days from the last dose of all study drug(s), or at the time of permanent treatment discontinuation if discontinuation is after the Safety Follow-Up Visit 1 window. Safety Follow-Up Visit 2 occurs 100 (\pm 7) days from the last dose of all study drug(s). Safety Follow-up Visits should occur regardless of initiation of subsequent anticancer therapy. Both Safety Follow-up Visits should be conducted in person.
- c. Survival Follow-Up to occur every 12 weeks (\pm 14 days) following the Safety Follow-Up Visit 2. Survival Follow-Up may be conducted in person or by telephone. The Sponsor may request that survival data be collected on all treated patients outside of the 3-month specified window. At the time of this request, each patient will be contacted to determine their survival status unless the patient has withdrawn consent for all contact. Information about subsequent anticancer therapy will also be collected during these contacts.
- d. Some of the assessments referred to in this section may not be captured as data in the eCRF. They are intended to be used for safety monitoring purposes by the treating physician. Additional testing or assessments may be performed as clinically necessary or where required by institutional or local regulations.

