Brain Imaging	
 Patients with a history of brain metastasis or neurological symptoms should have MRI with and without contrast. See Section 7.2 if patient has contraindications to contrast MRI. Performed on same schedule as body tumor assessments, and as clinically indicated Tumor assessments will continue until both BICR and Investigator’s assessments of tumor images have determined progression. Patients who are receiving study treatment beyond progression should continue scans until the criteria for treatment discontinuation are met and BICR-assessed progression has occurred. Tumor assessments are no longer required if subsequent anticancer therapy is started, even if the patient has not yet progressed. Use same imaging method as was used at screening. 						All study treatment decisions will be based on the Investigator’s assessment of tumor images. See Section 7.0 for further details.	
Pharmacokinetic and Biomarker Assessments								
	■				■	■		
NKTR-214 PK Blood Samples	X	X	X	X	X	Z	Z = Cycles 3, 6, 9, 12, and 15 only See Table 6 and Section 5.9 for further details.	
Nivolumab PK Blood Samples	X				X	Z	Z = Cycles 3, 6, 9, 12, and 15 only See Table 6 and Section 5.9 for further details.	
Tumor Tissue Sample							Optional Cycle 1 Day 14-21 and at disease progression. See Section 5.10.1 for further details.	

Abbreviations used in this table appear on the final page of Table 4.

Table 2: On-Treatment Schedule of Events for Arm A (Contd)

Procedure ^a	Arm A NKTR-214 0.006 mg/kg IV q3w and Nivolumab 360 mg IV q3w Cycle = 6 Weeks							Notes
	Cycle 1					Cycle 2 and all subsequent cycles		
	Day 1	Day 3 (-1 day)	Day 5 (± 1 day)	Day 8 (-1 day)	Day 22 (± 3 days)	Day 1 (± 3 days)	Day 22 (± 3 days)	
██████████ ██████████ ██████████ ██████████	■				■	■		████████████████████ ████████████████████ ████████████████████ ████████████████████ ████████████████████ ████████████████████ ████████████████████ ████████████████████ ████████████████████ ████████████████████
Outcomes Research Assessments								
EQ-5D-3L	X				X	X	X	Patients should complete the assessment at the start of the clinic visit, prior to dosing and scheduled activities.
FKSI-19	X				X	X	X	
PRO-CTCAE	X				X	X	X	Completed on Days 1 and 22 of every cycle through Cycle 4, and then on Day 1 of all subsequent cycles. See Section 7.6 for further details.
Health Care Resource Utilization	X				X	X	X	Site staff will collect health care resource utilization data using the CRF.

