The most common AEs considered by the Investigator to be related to NKTR-214 were fatigue (20 patients, 71.4%), flu-like symptoms (19 patients, 67.9%), pruritus (18 patients, 64.3%), hypotension (16 patients, 57.1%), rash (14 patients, 50.0%), decreased appetite (13 patients, 46.4%), and arthralgia or cough (9 patients, 32.1% each). Such treatment-related AEs as flu-like symptoms, rash and pruritus were generally mild or moderate in severity, predictable, manageable, and short-lived. These IL-2 mediated AEs generally occurred 3 to 4 days after dosing and corresponded to the time of peak plasma concentration of the active cytokines. The flu-like symptoms were managed with acetaminophen and non-steroidal anti-inflammatory drugs (NSAIDs) and the cases of rash/pruritus were either self-limiting or treated with anti-histamines (steroids were administered for occasional patients who had severe rash/pruritus).

The most frequently reported Grade ≥ 3 events were hypotension (5 of 28 patients, 17.9%), syncope (3 patients, 10.7%), metastases to central nervous system (3 patients, 10.7%), and abdominal pain, headache (1 of 2 related), and anemia (each: 2 patients, 7.1%).

Six of 28 patients reported Grade 3 treatment-related AEs, which included hypotension, abdominal pain, infusion-related reaction, headache, and syncope. The cases of Grade 3 hypotension were rapidly reversed with intravenous fluids, and a hydration management guideline was implemented during the study which mitigated the hypotension severity. One patient, who had a prior history of an infusion reaction to a previously administered immunotherapy, discontinued treatment due to an infusion-related reaction following the first dose of NKTR-214. With the exception of one event of hypothyroidism, no other immune mediated AEs consistent with checkpoint inhibitors were reported. No patient experienced capillary leak syndrome and no Grade 4 treatment-related AEs or treatment-related deaths were reported on the study.

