5.4.1.1 NKTR-214 Dosing

Each patient's NKTR-214 dose will be determined by the patient's weight in kilograms, which will be determined on the day of each NKTR-214 dosing. If the patient's weight is within 10% of the Cycle 1 Day 1 weight, the study drug doses do not need to be recalculated depending on institutional guidelines/preference. If the patient's weight has changed more than 10% from the Cycle 1 Day 1 weight, the dose of NKTR-214 must be recalculated and subsequent weight measurements should be compared with this new baseline weight to determine if further NKTR-214 dose recalculations are necessary.

Patients should receive NKTR-214 at a starting dose of 0.006 mg/kg on Day 1 and Day 22 of each treatment cycle until progression, unacceptable toxicity, withdrawal of consent, completion of 2 years (Arm A only) of treatment from Cycle 1 Day 1, the study ends, or other protocol-specified reasons in Section 5.4.3, whichever occurs first. Patients may be dosed no

less than 18 days from the previous dose. Study agent(s) should be administered in an area with access to resuscitation equipment.

NKTR-214 will be administered first, before nivolumab. NKTR-214 will be administered IV over 30 (\pm 5) minutes at a starting dose of 0.006 mg/kg every 3 weeks. The duration of infusion of NKTR-214 may be increased if necessary (e.g., patient history of infusion reaction) (see Pharmacy Manual for details).

Patients should be carefully monitored for infusion reactions during NKTR-214 administration. If an acute infusion reaction is noted, patients should be managed according to Section 5.13.9.

NKTR-214 treatment can continue for patients randomized to Arm A in the event that nivolumab is stopped due to toxicities.

[REDACTED]

Please refer to the Pharmacy Manual/current Investigator’s Brochure for details regarding NKTR-214 reconstitution, preparation, storage, and administration.

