5.4.1.2 Nivolumab Dosing

Nivolumab administration should start at least 30 minutes after the end of the NKTR-214 administration. Nivolumab will be administered IV over 30 (\pm 5) minutes at a dose of 360 mg. The duration of infusion of nivolumab may be increased if necessary (e.g., patient history of infusion reaction) (see Pharmacy Manual for details).

There will be no dose escalations or reductions of nivolumab allowed. Patients may be dosed no less than 18 days from the previous dose. Premedications are not recommended for the first dose of nivolumab.

Patients should be carefully monitored for infusion reactions during nivolumab administration. If an acute infusion reaction is noted, patients should be managed according to Section 5.13.9.

[REDACTED]

[REDACTED]

[REDACTED]

Instructions for dilution and infusion of nivolumab injection will be provided in the Pharmacy Manual.

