7.6.3 PRO-CTCAE

The PRO-CTCAE is a patient-reported outcome measure developed to evaluate symptomatic toxicity in patients participating in oncology clinical trials. It was designed to be used as a companion to the CTCAE, the standard lexicon for adverse event reporting in cancer trials. PRO-CTCAE includes an item library of 124 items representing 78 symptomatic toxicities drawn from the CTCAE. PRO-CTCAE provides a systematic yet flexible tool for descriptive reporting of symptomatic treatment side effects in cancer clinical trials. Selected items from the PRO-CTCAE will be administered. Patients will complete the PRO-CTCAE patient to the availability of language translations ([Basch, 2014](#)).

The PRO-CTCAE uses a recall period of “the last 7 days.”

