7.6 Health-Related Quality of Life (HRQoL)

Patients will be asked to complete the NCCN/FACT Symptom Index for Kidney Cancer (FKSI-19), 3-level version of the EuroQol Group's EQ-5D (EQ-5D-3L), and selected items from the Patient-Reported Outcomes version of the Common Term Criteria for Adverse Events (PRO-CTCAE).

Patients will complete the patient-reported outcome measures prior to any assessments at each clinic visit before randomization, prior to the first dose on Day 1 and 22 of every cycle through Cycle 4, and then on Day 1 of all subsequent cycles. In addition, the patient-reported outcome measures will be completed at designated time points during the follow-up period. The primary time points of interest will be Week 12, Week 24, and Week 48.

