7.6.3 PRO-CTCAE

The PRO-CTCAE is a patient-reported outcome measure developed to evaluate symptomatic toxicity in patients participating in oncology clinical trials. It was designed to be used as a companion to the Common Terminology Criteria for Adverse Events (CTCAE), the standard lexicon for adverse event reporting in cancer trials. PRO-CTCAE includes an item library of 124 items representing 78 symptomatic toxicities drawn from the CTCAE. PRO-CTCAE provides a systematic yet flexible tool for descriptive reporting of symptomatic treatment side effects in cancer clinical trials. Selected items from the PRO-CTCAE will be administered. The PRO-CTCAE uses a recall period of “the last 7 days.”

To report the PRO-CTCAE data, the tabulation of the maximum score post-baseline per patient per item will be used, and it will be presented by treatment group. A by-patient listing of PRO-CTCAE will also be provided.

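### Scheduled Arm A FKSI-19 and PRO-CTCAE forms do not reach back to the first week after an infusion, which leaves a gap in the patient-reported toxicity data

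*Protocol*

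**What the plan says.** Protocol 1.2, Table 2, marks EQ-5D-3L, FKSI-19 and PRO-CTCAE in Arm A on Days 1 and 22 only. The Cycle 1 columns for Days 3, 5 and 8 carry no questionnaire. The notes read "Completed on Days 1 and 22 of every cycle through Cycle 4, and then on Day 1 of all subsequent cycles" and "Patients should complete the assessment at the start of the clinic visit, prior to dosing and scheduled activities". SAP 7.6 applies the same timing to all the patient-reported measures: "prior to the first dose on Day 1 and 22 of every cycle through Cycle 4".

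Infusions fall on the same days. Protocol 5.4.1.1 states: "Patients should receive NKTR-214 at a starting dose of 0.006 mg/kg on Day 1 and Day 22 of each treatment cycle". Protocol 5.4.1.2 adds "Patients may be dosed no less than 18 days from the previous dose", and 5.4.1.1 has the same rule for NKTR-214. Protocol 7.6.1 and 7.6.3 give a 7-day recall for FKSI-19 and PRO-CTCAE.

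On symptom timing, Protocol 2.2.4 says: "These IL-2 mediated AEs generally occurred 3 to 4 days after dosing and corresponded to the time of peak plasma concentration". The same paragraph describes flu-like symptoms, rash and pruritus as short-lived. Protocol 5.13.4 puts the peak of active cytokine at Days 4 to 8, and 5.15.3.5 says the cytokine rise lasts about a week.

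On purpose and analysis, Protocol 7.6.3 says "The PRO-CTCAE is a patient-reported outcome measure developed to evaluate symptomatic toxicity in patients participating in oncology clinical trials". In SAP 7.6.3, "the tabulation of the maximum score post-baseline per patient per item will be used".

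**The concern.** A toxicity questionnaire is informative only if its recall window overlaps the days when toxicity is expected. Here the experimental drug is given in pulses. Its characteristic symptoms are expected within days of each pulse, and every post-baseline form is completed just before the next one. Taking the maximum score cannot recover this, because every Arm A form that enters the maximum has the same blind spot.

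What is at stake is interpretation. A low Arm A maximum for a flu-like or skin item could mean good tolerability, or it could mean only that the item was asked about at the end of the 3-week interval. The patient-reported data could not separate the two. The primary and key secondary endpoints are unaffected.

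**Working it through.** The plan states no figure to reproduce, so the check is interval arithmetic.

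**Inputs.** Infusion interval 21 days (Day 1 and Day 22 of a 42-day cycle); visit windows ±3 days; shortest dosing interval 18 days; recall 7 days; Safety Follow-Up Visit 1 at 30 ± 7 days after the last dose (Protocol 5.6.1); symptom onset at post-dose days 3 to 4.

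**Formula.** A form completed v days after the last infusion covers post-infusion days v − 7 to v.

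| Form | v | Days covered | Includes days 3–4? |
|---|---|---|---|
| On schedule | 21 | 14–21 | No |
| Shortest permitted interval | 18 | 11–18 | No |
| Visit 3 days late | 24 | 17–24 | No |
| Safety Follow-Up 1, earliest | 23 | 16–23 | No |
| Safety Follow-Up 1, nominal | 30 | 23–30 | No |

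The earliest day reached is 18 − 7 = day 11, and dose delays only push the window later. If the visit windows alone applied, without the 18-day rule, a visit at Day 25 followed by one at Day 40 would be 15 days apart. The form would then cover days 8 to 15 and still miss days 3 to 4. Cycle 1 Day 1 is excluded because it precedes any infusion.

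**Main time points.** SAP 7.6 names Weeks 12, 24 and 48. With 6-week cycles, 12/6 = 2, 24/6 = 4 and 48/6 = 8 completed cycles, so these are Day 1 of Cycles 3, 5 and 9. All three are pre-dose in Arm A.

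**Arm B.** Cabozantinib is continuous, so apart from interruptions its recall windows are on drug. Sunitinib is taken on cycle days 1 to 28 and stopped on days 29 to 42. A Day 22 form (Days 19 to 25 with the window) reaches back to day 19 − 7 = 12 at the earliest, which is on drug. A Day 1 form covers about days 36 to 42 of the previous cycle, which is off drug. After Cycle 4 only Day 1 forms remain. The PRO-CTCAE maximum therefore includes on-drug forms for cabozantinib, and for sunitinib through Cycle 4, but no Arm A form from the post-infusion week.

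**Effect of a Day 8 form.** Cycle 1 Day 8 (−1 day) exists in Tables 2 and 3, with vital signs and central laboratory tests but no questionnaires. At v = 7 the form covers days 0 to 7. At v = 6 it covers from the day before the infusion to day 6. Both include days 3 and 4.

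**The case against.** The strongest reply is that these events are not lost. Table 2 collects adverse events continuously and records them at each visit, including the Arm A Day 3, 5 and 8 visits in Cycle 1. Protocol 5.4.2.2 requires site contact 2 to 4 days after each of the first two infusions, with symptoms documented. SAP 8.3.2 analyses flu-like symptoms, rash and pruritus, fatigue, arthralgia and other categories by grade and by 3-week cycle. All of this stands. It limits the gap to what patients themselves report, which Protocol 7.6 gives as the reason for collecting these measures alongside physician reporting.

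The endpoint also ranks low. PRO-CTCAE receives a tabulation and a listing with no test. FKSI-19 does have a between-arm mixed model, but outside the alpha-controlled hierarchy, and its stated objective is cancer-related symptoms and quality of life. That stands too, although FKSI-19 includes a treatment side effects subscale.

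A reader might infer that the trial could show favourable tolerability for NKTR-214 through timing alone, with comparator toxicity captured and experimental toxicity missed. The documents do not support that. The adverse event analyses are unaffected, and sunitinib Day 1 forms are themselves off drug. The TKI mix is not given. The protocol does not apply its short-lived description to fatigue, decreased appetite or arthralgia. Symptom durations are not stated, and a symptom lasting past about day 11 to 14 would be reported. The selected PRO-CTCAE items are not listed, so it cannot be checked which of these symptoms are asked about.

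**Conclusion.** The scheduling point holds. From Cycle 1 Day 22 onward, no scheduled Arm A FKSI-19 or PRO-CTCAE form reaches back before about post-infusion day 11, and overlap with days 3 to 4 is zero in every permitted case. This rests on forms being completed at the visits marked and on the stated 7-day recall.

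The number of patients whose symptoms would be missed cannot be calculated. In the monotherapy study of 28 patients (Protocol 2.2.4), flu-like symptoms occurred in 71.4%, pruritus in 67.9% and rash in 53.6%; the treatment-related rates were 67.9%, 64.3% and 50.0%. These pool doses from 0.003 to 0.012 mg/kg and include a 2-weekly schedule, so they show only that such symptoms are common. The share resolving before day 11 is not given. The direction and size of any net between-arm bias are likewise unknown. This is a limitation of the patient-reported toxicity data that is worth a cheap improvement, not a threat to the trial's conclusions on efficacy or on investigator-reported safety.

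**What to change.** 1. In Protocol Tables 2 and 3, add PRO-CTCAE and FKSI-19 at the existing Cycle 1 Day 8 (−1 day) visit in both arms.
2. In SAP 7.6, tabulate the Day 8 scores separately by arm. Protocol 9.5 already plans summaries at each assessment point.
3. Keep the planned PRO-CTCAE maximum-score table without Day 8, and give a version including it as supplementary only. Pooling Day 8 into the main table would set Arm A at its expected symptom peak against Arm B after one week of a daily oral drug, which could create an imbalance the other way.
4. State in the SAP that the scheduled Day 1 and Day 22 forms do not cover the post-infusion week in Arm A.

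The cost is a few minutes of patient time at a visit already attended, plus table and SAP wording. The fix is partial. Day 8 exists in Cycle 1 only, so just the first infusion is covered, and patients already past Cycle 1 would not contribute.

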5.6.1 Safety Follow Up

- Safety Follow-up Visit 1 should occur 30 (± 7) days from the last dose of all study drug, or at the time of permanent treatment discontinuation if discontinuation is after the Safety Follow Up Visit 1 window.
- Safety Follow-up Visit 2 occurs 100 (± 7) days from the last dose of all study drug. Safety follow-up visits should occur regardless of initiation of subsequent anticancer therapy.
- Both Safety Follow-Up Visits should be conducted in person.
- Per clinical judgment, the patient may come in earlier for additional follow up.

- Patients will also be followed for safety until resolution or permanent sequelae of all toxicities attributable to study drugs (NKTR-214 and/or nivolumab or TKI) as outlined in Sections 8.5 and 8.8.
- For AE and SAE reporting periods, please refer to Sections 8.5 and 8.7.

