For patients off treatment, the treatment-emergent period is defined as the period of time on or after the day (and time, if collected and not missing) of the first dose of study treatment, until: the date of (initiation of new anticancer therapy – 1 day) or (30 days after the date of the last dose of any study treatment), whichever is earlier.

The extended treatment-emergent period will be defined as the period of time on or after the day (and time, if collected and not missing) of the first dose of study treatment until earlier date of (initiation of new anticancer therapy – 1 day) and (100 days after the date of the last dose of any study treatment).

- **Treatment-Emergent Adverse Event (TEAE):**

TEAEs are AEs with an onset date (and time, if collected and not missing) within the treatment-emergent period, or extended treatment-emergent period depending on the analysis

Incomplete start and end dates for TEAEs will be imputed. Any AE will be considered as a TEAE if its status cannot be fully determined because of incomplete data.

- **Last Known Alive Date:** Last known alive date will be defined as the latest alive date on or before data cutoff date, captured from multiple sources. Note that if there is an event date (either an assessment or death) beyond the data cutoff date, the last known alive date will be the data cutoff date. If a patient died before or on the data cutoff date, the last known alive date will be set as the death date. The last known alive date will not be imputed, except in the case that the death date is partially missing (see details in Section 6.4)

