8.5.1 Hematology

The following will be summarized by treatment group as baseline CTC grade and worst CTC grade on-treatment per patient: hemoglobin, platelet, white blood counts (WBC), absolute neutrophils count (ANC) and lymphocyte count (LYMP). A table presenting number and percentage of patients with post-baseline CTC grade increased from baseline (any grade, grade 3-4) by treatment group will be provided.

The analyses will be conducted using the treatment-emergent period.

A by-patient listing of these laboratory parameters will be provided.

Eosinophil (EOS)

- Summary of baseline and highest post-baseline EOS will be provided by treatment group:
 - Mean (standard deviation [SD] and standard error [SE]), median, min and max
 - Percent exceeding thresholds: $\geq 10 \times 10^9/L$, $\geq 5 \times 10^9/L$, $\geq 1.5 \times 10^9/L$
 - Time to highest post-baseline EOS: mean (standard deviation [SD]), median, min, max
 - Duration (Weeks) of Sustained Eosinophils $\geq 1.5 \times 10^9/L$: % of patients with eosinophils returned, % patients with duration longer than 6 months, median and 95% CI will be estimated using the KM method

Plot of mean eosinophil (\pm SE) by treatment arm and time.

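### SAP 6.6 closes the lab analysis period at last dose + 30 days, but Safety Follow-Up Visit 1 may fall on Day 37 or later, so protocol-compliant Visit 1 labs drop out of four sets of tables

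*Protocol*

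**What the plan says.** **Visit timing.** Protocol 5.6.1 states: "Safety Follow-up Visit 1 should occur 30 (± 7) days from the last dose of all study drug". Table 4, footnote b, in Section 1.2 adds the alternative: "or at the time of permanent treatment discontinuation if discontinuation is after the Safety Follow-Up Visit 1 window". For the second visit, Protocol 5.6.1 states: "Safety Follow-up Visit 2 occurs 100 (± 7) days from the last dose of all study drug". Both visits take place whether or not new anticancer therapy has begun.

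**Labs at those visits.** Table 4 schedules central laboratory testing at Visit 1 for everyone. At Visit 2 it is conditional: "During Safety Follow-up Visit 2 if toxicities are present".

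**Analysis periods.** SAP 6.6 leaves the treatment-emergent period open for patients still on treatment. For patients off treatment it ends at "30 days after the date of the last dose of any study treatment", or on the day before new anticancer therapy if that is earlier. The extended period ends at "100 days after the date of the last dose of any study treatment", with the same truncation. Neither limit includes a visit window.

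**Tables.** SAP 8.5.1 (hematology) states: "The analyses will be conducted using the treatment-emergent period". The same rule governs chemistry (8.5.2), electrolytes (8.5.3) and the thyroid part of 8.5.4. Only the abnormal hepatic function table in 8.5.4 uses the extended period. SAP 8.5 also limits each laboratory population to patients who have a baseline value and at least one treatment-emergent value.

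**The concern.** The protocol and the SAP use the same nominal days, 30 and 100, but only the protocol gives them a tolerance. A site that sees a patient on Day 33 has followed the protocol, yet the SAP places that sample outside the period. Whether a scheduled safety lab is counted then depends on the calendar day of the appointment and on nothing clinical.

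The visit affected is the one post-treatment lab draw that every patient is meant to have. Patients whose permanent discontinuation is declared after Day 37 lose their Visit 1 labs from the 30-day tables by rule, however promptly the site acts. What is at stake is completeness of the worst-grade and shift summaries and of the thyroid table. Protocol 2.3.5 lists serum creatinine elevation and thyroid dysfunction among the identified risks of NKTR-214, and both are tabulated on the 30-day period.

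**Working it through.** The plan states no figure for labs excluded, so there is nothing to reproduce. The check compares day counts, with day number meaning days after last dose.

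**Inputs.** Visit 1: 30 ± 7 days, or at a later permanent discontinuation (Protocol 1.2 and 5.6.1). Visit 2: 100 ± 7 days (same places). Cut-offs: 30 and 100 days (SAP 6.6). Arm A dosing delay that generally requires discontinuation: more than 8 weeks from the previous dose, with exceptions (Protocol 5.14.1.1).

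**Visit 1, in window.**
- Permitted days: 30 − 7 = 23 to 30 + 7 = 37, which is 37 − 23 + 1 = 15 days.
- Days past the cut-off: 31 to 37, which is 37 − 30 = 7 days.
- Share of permitted days: 7/15 = 46.7%.

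This is a share of days, not of visits. Converting it needs an assumption about visit timing:
- Uniform over the window: 46.7% of in-window visits.
- Triangular around Day 30, weight 8 − |d − 30|: total weight 8 + 2 × (7 + 6 + 5 + 4 + 3 + 2 + 1) = 64; weight on Days 31-37 is 28; 28/64 = 43.8%.
- No assumption: anywhere from 0% to 100%.

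**Visit 1 at a late stop decision.** If treatment is stopped as soon as a delay exceeds 8 weeks, Visit 1 falls on about Day 57. That is 57 − 30 = 27 days past the cut-off and 57 − 37 = 20 days past the visit window. Every Visit 1 lab after Day 37 is excluded from the 30-day tables. A lab on Day 42 of such a hold is excluded too, once the patient counts as off treatment. Day 57 is still inside the 100-day period.

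**Visit 2.** Permitted days are 93 to 107, and Days 101-107 are again 7 of 15. These labs are conditional, and the 100-day limit currently governs only the hepatic table.

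**Where each lab ends up, absent new anticancer therapy:**

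| Sample | 8.5.1-8.5.3 and thyroid tables | Abnormal hepatic function table | Listings |
|---|---|---|---|
| Visit 1, Days 23-30 | in | in | in |
| Visit 1, Days 31-37 | out | in | in |
| Visit 1 at a stop decision, e.g. Day 57 | out | in | in |
| Visit 2, Days 93-100, if drawn | out | in | in |
| Visit 2, Days 101-107, if drawn | out | out | in |

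The hepatic column applies to the liver tests only. Those same analytes are also graded in 8.5.2, where the 30-day limit applies.

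**The case against.** The strongest reply is that little information is lost. The grade tables report the worst on-treatment grade per patient, so an excluded sample matters only if it would have set that grade. All safety data are listed (SAP 8.0). Clinically significant results are recorded as adverse events (Protocol 8.15), which are collected for 100 days (Protocol 8.2). Drug-related events are re-tabulated on the extended period (SAP 8.1), and Arm A endocrine immune-mediated events use that period as well (SAP 8.2.2). Arm A patients on hold are re-evaluated at least weekly (Protocol 5.13) and may have labs inside Day 30. All of this stands and limits the harm. None of it explains why a sample taken on schedule should be excluded. The SAP does allow for visit timing elsewhere: its missed-scan rule in 7.5.2.1 adds 14 days.

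A reader might infer more than the documents support:
- *The hepatic table understates Visit 1 abnormalities.* It does not. Its 100-day period keeps Visit 1 liver tests, including those from a Day 57 stop.
- *Nearly half of all Visit 1 labs are lost.* The 44-47% figures rest on assumed visit timing.
- *The loss falls more heavily on Arm A.* This is not shown. Arm B visits stay fixed during holds with all assessments performed (Protocol 5.13), so Arm B labs taken after Day 30 of a hold that ends in discontinuation are cut too.
- *Vital signs are affected.* SAP 8.6.1 summarises them by scheduled visit with no stated cut-off.
- *Adverse events are dropped by the visit window.* They are classified by onset date, not visit date.

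**Conclusion.** The mismatch is real and follows from the stated rules without any assumption. Compliant Visit 1 labs on Days 31-37, and all Visit 1 labs taken at a stop decision after Day 37, are excluded from the hematology, chemistry, electrolyte and thyroid tables. In days, this is 7 of the 15 permitted. The share of visits, the number of late stop decisions and the effect on any worst-grade count cannot be estimated from the documents. The Visit 2 mismatch is minor: it concerns conditional labs in one table. No claim of bias between arms is supported. This is an inexpensive correction worth making, and it does not put the safety conclusions in doubt.

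**What to change.** In SAP 6.6, for laboratory data only, end the treatment-emergent period at last dose + 37 days and the extended period at last dose + 107 days. Keep truncation on the day before new anticancer therapy, and keep 30 and 100 days for adverse-event onset. Vital signs need no change.

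A 37-day limit still misses Visit 1 labs from a late stop decision. Ending each patient's period at the actual Visit 1 date would capture them, but the window would then depend on the length of the hold. It is better to repeat the 8.5.1-8.5.3 and thyroid tables on the extended period already used for the hepatic table. These repeats should be labelled supplementary, because any Visit 2 samples in them were drawn only when toxicities were present. A stop decision later than Day 107, possible under the exceptions to the 8-week rule, would still appear only in listings.

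The cost is SAP wording, one programming parameter and a small set of extra tables. The downside is a lab window one week longer than the adverse-event window, which a footnote can explain. Trial conduct is unaffected.
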